- 17.** For women of child-bearing potential, serum pregnancy testing must be performed within 72 hours prior to C1D1 and at End of Treatment visit. In addition, urine pregnancy tests will be performed pre-dose on Day 1 of each cycle. If any urine test result is positive, patient dosing will be postponed until the result is confirmed by a serum pregnancy test. Patients with a positive serum test will be discontinued from the study.
- 18.** Includes insertion of central venous access device, if not already present (if NUC-1031 is centrally administered).
- 19.** Optional fresh biopsy tissue sample collection within 24 hours post administration of C1D1 dose for patients who consent.
- 20.** Includes treatment discontinuation due to disease progression or early treatment discontinuation for other reasons (*e.g.* withdrawal of consent). Progressive disease should be confirmed prior to stopping treatment. Visit to occur within 30 (± 7) days of the last dose of NUC-1031.
- 21.** Patients withdrawing from the study with no radiological evidence of disease progression will receive scans every 8 weeks (± 7 days) from C1D1 until disease progression, initiation of a new treatment or death in order to determine duration of overall response and PFS.
- 22.** Adverse events should be captured from the time of consent up to 30 days after the last dose of NUC-1031. SAEs deemed definitely, probably or possibly related to NUC-1031 but outside of this window (>30 days from last dose of NUC-1031) should also be captured in the eCRF.
- 23.** Patients with evidence of disease progression as defined by RECIST criteria will receive a phone call at regular intervals (every 12 weeks ± 7 days) until death, loss to follow-up, or study discontinuation in order to determine duration of Overall Survival.

ABBREVIATIONS

°C	Degrees Centigrade
AE	Adverse event
ALT	Alanine aminotransferase
ANC	Absolute neutrophil count
AST	Aspartate aminotransferase
AUC	Area under the curve
AUC _{0-t}	Area under the plasma concentration-time curve from time zero to the last measurable concentration
BICR	Blinded Independent Central Reviewer
BRCA 1/2	Breast cancer (gene) 1/2
BUN	Blood urea nitrogen
CA125	Cancer Antigen 125
CDA	Cytidine deaminase
CL	Apparent clearance
C _{max}	Maximum plasma concentration; peak plasma concentration
CNS	Central Nervous System
CR	Complete Response
CRF	Case report form
CRO	Clinical Research Organization
CSR	Clinical study report
CT	Computed tomography

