3.4 Duration of Patient Participation

Patients will continue to receive NUC-1031 until the occurrence of disease progression by RECIST or unmanageable drug-related adverse events despite dose modification. Patients may also decline treatment at any time for any reason, or they may meet any of the other reasons for treatment withdrawal defined in [Section 6.1](#). Reasons for treatment discontinuation must be captured in the patient medical record and on the Treatment Discontinuation page of the CRF.

Should a patient discontinue treatment without radiological evidence of disease progression, the patient should continue to undergo tumor assessment every 8 weeks from C1D1 until such time as progression can be documented or new treatment is initiated.

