5.5.8 Follow-Up

Patients who stop treatment with no evidence of disease progression as defined by RECIST criteria will continue to receive scans at regular intervals (every 8 weeks [± 7 days] from C1D1) until disease progression or death (whichever comes first) in order to determine duration of overall response and PFS.

Patients with evidence of disease progression as defined by RECIST criteria will receive a phone call at regular intervals (every 12 weeks [± 7 days]) until death, loss to follow-up, or study discontinuation in order to determine duration of Overall Survival.

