6.2 Follow-Up After Treatment Discontinuation

Patients who have documented disease progression defined by RECIST criteria while receiving study medication will discontinue treatment but will enter the follow up period. Patients should not discontinue NUC-1031 because of raised CA125 or other clinical signs of PD until PD has been confirmed by RECIST.

Patients who stop treatment with no evidence of disease progression will enter the follow-up period and should attend clinic every 8 weeks (± 7 days) from C1D1 for follow-up scans and assessments. This should continue until disease progression, initiation of a new treatment or death.

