11 TUMOR RESPONSE ASSESSMENTS

11.1 Tumor Measurements and Assessment of Disease Response

Patients must have at least one lesion that can be accurately assessed at baseline by CT, MRI or PET-CT (US only), which is suitable for repeated assessment in order to be eligible for this study. All known or suspected disease sites must be assessed at baseline by either CT, MRI or PET-CT (US only) scan. The same radiological methods at baseline must be used to follow lesions throughout the study. Disease must be measured according to RECIST criteria, with target and non-target lesions identified, measured and followed throughout the study ([Appendix 2](#)). Biopsied lesions should not be designated as target lesions for the purposes of RECIST.

Whenever possible, the same qualified physician will interpret results to reduce variability. Radiographic images will be maintained at the study center, and Investigator's findings will be filed in the patient's source documents.

In addition, digital copies of all radiographic images will be collected and stored in a central radiologic facility in order to allow for independent confirmation of the radiographic imaging results. Instructions for the collection, and submission of images are provided in a separate Imaging Manual.

Tumor measurements and disease response assessments are to be performed every 8 weeks (± 7 days) from C1D1. If the patient stops study treatment for reasons other than radiologically confirmed PD, tumor measurements and disease response assessments should continue every 8 weeks (± 7 days) from C1D1 thereafter until PD is radiologically confirmed.

Tumor measurements and disease response assessments also are to be performed any time disease progression is suspected.

Patients should not discontinue NUC-1031 because of raised CA125 or other clinical signs of PD until PD has been confirmed by RECIST.

CRs and PRs must be confirmed by repeated images at least 4 weeks after initial documentation.

In the case of SD, measurements must have met the SD criteria at least once after study entry at a minimum interval of not less than 6 weeks.

A third-party central imaging vendor will review all study-related imaging. The imaging vendor will not be responsible for assessing images in real-time to inform on patient treatment decisions. This responsibility will remain with the Principal Investigator at the site. Please refer to the Imaging Manual for details on submission and review of images.

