13.5.4 Efficacy Analysis

The primary response evaluation is based upon the determination of response using RECIST ([Appendix 2](#)) by a BICR:

- **ORR** is defined as the number of patients achieving a confirmed response (CR or PR). Number and percentage of patients achieving a response, with confidence intervals, will be provided. In addition, the number and percentage of patients achieving individual best response criteria of CR, PR, SD, PD, or NE will be described.
- **Change from baseline in tumor size** is measured as the percentage change in the total measurements of target lesions from the pre-treatment scan, measured at each scheduled scan.
- **Duration of Overall Response** is measured from the time measurement criteria are first met for CR or PR (whichever is first recorded) until the first date that recurrent or PD is objectively documented (taking as reference for PD the smallest measurements recorded since the treatment started). Only responses that were later confirmed, will be considered when calculating the DoR. For patients who were lost to follow-up without progression or reached the time point of analysis without a known record of death or progression, the duration of response will be censored at the date of last tumor assessment.
- **PFS** is defined as the time from the date of study treatment initiation (start of treatment) to the first date of objectively determined PD or death from any cause. For patients who are still alive at the time of the data cut-off date and without evidence of tumor progression, PFS will be censored at the date of the most recent objective progression-free observation. For patients who receive subsequent anticancer therapy prior to objective disease progression or death, PFS will be censored at the date of the last objective progression-free observation prior to the date of subsequent therapy.

The number of overall censored patients, number of patients with events and Kaplan-Meier estimates median time will be provided. In addition, the results will be presented graphically in Kaplan-Meier plots.

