- **Time to Disease Progression** is measured from the start of the treatment until the criteria for progression are first met, taking as reference the smallest measurements recorded since the treatment started, including the baseline measurements. For patients who were lost to follow-up, or died without progression or reached the time point of analysis without a known record of progression, the time to progression will be censored at the date of last tumor assessment.

The number of overall censored patients, number of patients with events and Kaplan-Meier estimates median time will be provided. The results will also be presented graphically in Kaplan-Meier plots.

- **Disease Control Rate** is defined as the number of patients achieving confirmed response (CR or PR) or SD as best overall response (as defined in RECIST).
- **Best GCIG Overall Response** (CR, PR, SD, PD, NE): number and percentage of patients with responses defined per GCIG criteria will be described.
- **OS** is defined as the time from randomization until death from any cause. All deaths will be included, whether they occur during the study or following treatment discontinuation. For patients who have not died, overall survival will be censored at the date of last contact.

The number of overall censored patients, number of patients with events and Kaplan-Meier estimates median time will be provided. In addition, the results will be presented graphically in Kaplan-Meier plots.

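### The protocol conflicts on whether scans stop at a new therapy, and only PFS is censored there, so duration of response and TTP depend on which section a site follows

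*Protocol*

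**What the plan says.** **When scans stop.** Four places end imaging when another treatment begins, for a patient who has stopped NUC-1031 without progression:

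- Schedule of Events, note 21: "until disease progression, initiation of a new treatment or death in order to determine duration of overall response and PFS".
- Section 3.4: "until such time as progression can be documented or new treatment is initiated".
- Section 5.5.6: the heading itself names a new treatment as a stopping point.
- Section 6.2: "This should continue until disease progression, initiation of a new treatment or death".

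Three places leave that stop out:

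- Section 5.5.8: "until disease progression or death (whichever comes first) in order to determine duration of overall response and PFS".
- Section 11.1: "from C1D1 thereafter until PD is radiologically confirmed".
- Schedule of Events, imaging row: progression only. The row carries note 13; note 21 is attached to the follow-up visit column.

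**How the endpoints treat a new therapy.** All three rules are in 13.5.4.

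- PFS has an explicit rule: "For patients who receive subsequent anticancer therapy prior to objective disease progression or death, PFS will be censored", with the censoring date set at the last scan without progression before the new therapy.
- TTP is censored at the last tumor assessment. Its list of cases is "For patients who were lost to follow-up, or died without progression or reached the time point of analysis without a known record of progression".
- Duration of response is also censored at the last tumor assessment, for loss to follow-up or no known event by the time of analysis.

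New therapy is in neither the TTP nor the duration-of-response list.

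**The concern.** Sections 5.5.8 and 6.2 cover the same patients on the same 8-week calendar but give different stopping points, so a site cannot follow both. Section 5 sends the reader to the Schedule of Events for detail, and there the imaging row and note 21 also differ. About 30 sites are planned, so uneven practice is foreseeable.

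The situation will arise. Section 6.1 allows treatment to end for toxicity, lack of further benefit, intercurrent illness or patient choice, and some of these patients will start another drug before progression.

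The two gaps act together. If scans stop at the switch, the last tumor assessment falls just before it and little harm follows. If they continue, a progression first seen on the next drug becomes the TTP or duration-of-response event, or a later clean scan becomes the censoring date. Both endpoints are meant to describe NUC-1031 activity at the selected dose, with no control arm against which to judge the contribution of the next therapy.

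**Working it through.** The protocol states no figure on this point, so there is none to reproduce. The check has four steps. Steps 1, 3 and 4 are illustrations on assumed data.

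**1. One patient under each reading.** Assume response at the week 8 scan, confirmed at week 16; NUC-1031 stopped for toxicity; new therapy at week 18; progression at week 48.

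| | Site follows 5.5.8 or 11.1 | Site follows 6.2, 3.4, 5.5.6 or note 21 |
|---|---|---|
| PFS | censored, week 16 | censored, week 16 |
| TTP | event, week 48 | censored, week 16 |
| Duration of response | event, 48 − 8 = 40 weeks | censored, 16 − 8 = 8 weeks |

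This shows that the rules diverge. It does not measure a typical effect. The patient spends 48 − 18 = 30 weeks progression-free on the next drug, whereas section 1.2 gives a median time to progression of 3-4 months (about 13-17 weeks) in platinum-resistant disease.

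**2. Number of responders.** At an ORR of 10%, 44 × 0.10 = 4.4; at the 15% used in section 13.1, 44 × 0.15 = 6.6. So about 4-7 patients carry the duration-of-response estimate.

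**3. Effect on median TTP.** Inputs:

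- true median 3, 3.5 or 4 months (range from section 1.2);
- share q switching before progression, 10-30% (assumed);
- progression hazard after the switch relative to before, h, from 0.5 to 1.3 (assumed).

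With exponential times and switching unrelated to prognosis, λ = ln 2 / median and μ = qλ/(1 − q). If scans continue and TTP is not censored at the switch,

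S(t) = exp(−(λ+μ)t) + μ[exp(−hλt) − exp(−(λ+μ)t)] / (λ + μ − hλ).

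Solving S(t) = 0.5 gives the median in months:

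| True median | q | h = 0.5 | h = 0.7 | h = 1.0 | h = 1.3 |
|---|---|---|---|---|---|
| 3.0 | 10% | 3.07 | 3.04 | 3.00 | 2.97 |
| 3.0 | 20% | 3.15 | 3.08 | 3.00 | 2.93 |
| 3.0 | 30% | 3.26 | 3.14 | 3.00 | 2.89 |
| 3.5 | 10% | 3.58 | 3.54 | 3.50 | 3.46 |
| 3.5 | 20% | 3.68 | 3.60 | 3.50 | 3.42 |
| 3.5 | 30% | 3.81 | 3.66 | 3.50 | 3.37 |
| 4.0 | 10% | 4.09 | 4.05 | 4.00 | 3.96 |
| 4.0 | 20% | 4.20 | 4.11 | 4.00 | 3.91 |
| 4.0 | 30% | 4.35 | 4.19 | 4.00 | 3.86 |

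For h of 0.5-0.7 the rise is 0.04 (3.04 − 3.00) to 0.35 months (4.35 − 4.00). At h = 1 nothing changes. At h = 1.3 the median falls by 0.03 (3.00 − 2.97) to 0.14 months (4.00 − 3.86). Under this model, censoring at the switch returns the true median in every cell.

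**4. Direction for duration of response.** Assume four responders. Three have events at 40, 48 and 56 weeks. The fourth responds at week 8, has a last scan before new therapy at week 16, and progresses on the new therapy at week 24.

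- Without the rule, the fourth is an event at 24 − 8 = 16 weeks. Kaplan-Meier survival is 0.75 at 16 weeks and 0.50 at 40, so the median is 40 weeks.
- With the rule, the fourth is censored at 8 weeks. Survival is 2/3 at 40 weeks and 1/3 at 48, so the median is 48 weeks.

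One patient moves the median by 8 weeks, and here censoring lengthens it.

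**The case against.** The case on the other side has real force.

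- **The omission looks like drafting.** Sections 5.5.8 and 11.1 do not mention new therapy, and note 21 gives the same purpose as 5.5.8 while including the stop. A reader might infer a deliberate instruction to image through the next line; the text does not support that. The passages still conflict, and nothing says which one governs.
- **Censoring detail often sits in the SAP.** Section 13 says it gives only the main features. A SAP rule censoring TTP and duration of response at new therapy would remove the effect on those estimates. However, the protocol is not silent here: it recognises the event, writes a rule for PFS and gives the other two endpoints different lists. A SAP also cannot undo scans that some sites took and others did not, so an analysis that ignored later therapy would rest on uneven data.
- **Counting events regardless of later therapy is a legitimate choice.** That is so, but it needs scanning to continue in everyone, and four places stop it.
- **Exposure is limited.** Sections 6.1 and 6.2 discourage stopping for CA125 or clinical signs before RECIST progression. PFS has its own rule. Appendix 2 confines best response to the treatment period, which largely protects the primary ORR. TTP and duration of response are descriptive, with no test or decision attached.

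A reader might also infer that the gap always flatters NUC-1031. Steps 3 and 4 of the working show otherwise: the median can stay the same or fall, because an observation that would have been censored can become an early event.

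**Conclusion.** The point stands as an internal contradiction with consequences for two secondary endpoints. Seven places give scan-stop rules that split four to three on new therapy, and 13.5.4 treats the same event differently for PFS than for TTP and duration of response. As written, both estimates depend partly on which passage each site used, and one patient can be censored for PFS yet be a later event for TTP.

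The protocol gives neither the share of patients switching nor the next-line effect, so size and direction are unknown. The illustrated rise of up to about 0.35 months in median TTP rests on assumed values for both, and on switching being unrelated to prognosis. Duration of response is more fragile because so few patients carry it. The 40-week and 8-week figures for a single patient should not be read as a typical effect.

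The primary endpoint is not in doubt on this account. The correction is worth making because it is cheap and the durability data will be read without a comparator.

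**What to change.** 1. Reconcile the scan-stop wording in 5.5.8, 11.1 and the Schedule of Events imaging row with note 21, 3.4, 5.5.6 and 6.2, so that every place gives the same end of imaging: progression, start of a new anticancer therapy, or death.
2. In 13.5.4, extend the PFS rule to TTP and duration of response: where another anticancer therapy starts before progression, censor at the last progression-free tumor assessment before that therapy.

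The cost is a change of wording in three conduct passages and two endpoint definitions, and a few more censored observations. Whether the estimates become longer or shorter cannot be said in advance.

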6 PATIENT WITHDRAWAL

6.1 End of Treatment

Treatment with NUC-1031 is to be continued until one of the following occurs:

- Progressive Disease (PD) as defined by RECIST criteria. Patients should not discontinue NUC-1031 because of raised CA125 or other clinical signs of PD until PD has been confirmed by RECIST.
- Unmanageable toxicity defined as an AE that is considered by the Investigator to warrant permanent discontinuation of NUC-1031 including the following:
 - AE resulting in a dosing delay of more than 14 days in starting the next cycle, unless the patient is receiving clinical benefit.
 - Clinically significant drug-related AE that recurs despite dose reduction in two consecutive cycles. Patients may continue to receive treatment if the Principal Investigator and Medical Monitor agree that the patient is receiving a clinical benefit and the toxicity is manageable, reversible or transient.
- Lack of further clinical benefit or unfavorable risk/benefit profile as judged by the Investigator.
- Inter-current illness that prevents further administration of NUC-1031.
- Patient withdraws consent from further treatment or for further data collection.
 - If the patient withdraws consent for further treatment, follow-up visits should continue.
 - If the patient withdraws consent for further treatment and data collection, then no additional study visits or data collection should occur.
- Patient requires use of a prohibited concomitant medication or therapy.
- Pregnancy.
- Changes in the patient's condition, which in the opinion of the Investigator, make the patient unsuitable for further treatment with NUC-1031.
- Patient non-compliance.
- Lost to follow-up.
- Patient withdrawal of consent.
- Sponsor request.

All study procedures outlined for the End of Treatment visit are to be completed within 30 days (± 7 days) of the last dose of study drug. The primary reason for study drug discontinuation is to be recorded in the CRF.

6.2 Follow-Up After Treatment Discontinuation

Patients who have documented disease progression defined by RECIST criteria while receiving study medication will discontinue treatment but will enter the follow up period. Patients should not discontinue NUC-1031 because of raised CA125 or other clinical signs of PD until PD has been confirmed by RECIST.

Patients who stop treatment with no evidence of disease progression will enter the follow-up period and should attend clinic every 8 weeks (± 7 days) from C1D1 for follow-up scans and assessments. This should continue until disease progression, initiation of a new treatment or death.

6.3 Consent Withdrawal

Patients will be informed that they have the right to withdraw from the study at any time for any reason, without prejudice to their medical care.

Consent withdrawal means that a patient has expressed a wish to withdraw from the study altogether. Under these circumstances, the site personnel should document all relevant discussions in the patient notes and mark all future CRF pages as not applicable. Under these conditions, Investigators are still responsible to follow up any SAEs until resolution.

6.4 Patient Evaluability and Replacement

Enrollment will continue until there are 44 patients evaluable for a response assessment at the selected dose level. All patients with measurable disease (defined by BICR) will be considered evaluable for response assessment.

All eligible patients who receive at least one dose of NUC-1031 are considered evaluable for safety analysis.

7 SAMPLES FOR LABORATORY ANALYSIS

7.1 Clinical Laboratory Tests

All clinical laboratory testing will be performed at local sites. A serum or urine pregnancy test will be performed in women of child-bearing potential at the Screening visit. Laboratory tests may be performed either on the day of a treatment visit, or during the 3 days prior to a treatment visit.

7.2 Pharmacokinetics

PK sampling (blood and urine) will be performed at a sub-set of sites specified by NuCana. The PK schedule is designed to explore the relationship between NUC-1031 PK, pharmacodynamics and clinical activity. PK endpoints will include assessments of:

- In plasma/urine: NUC-1031, dFdC and dFdU.
- In PBMCs: NUC-1031, dFdC, dFdCMP, dFdCDP, dFdCTP and dFdU.

Blood samples will be collected at the following visits:

- Cycle 1: Days 1 and 2
- Cycle 1: Days 15 and 16
- Cycle 3: Days 1 and 2

The PK blood sampling schedule is summarized in [Table 1](#) below:

Table 1 PK sampling schedule

Sample 1	T ₀ – pre-dose (before the start of the infusion)
Sample 2	T ₁ – end of infusion
Sample 3	T ₂ – T ₁ plus 10 minutes
Sample 4	T ₃ – T ₁ plus 30 minutes
Sample 5	T ₄ – T ₁ plus 1 hour
Sample 6	T ₅ – T ₁ plus 2 hours
Sample 7	T ₆ – T ₁ plus 4 hours
Sample 8	T ₇ – T ₁ plus 6 hours
Sample 9	T ₈ – T ₁ plus 24 hours

Optional pooled urine collection for PK analysis will be taken 0-6 and 6-24 hours from the beginning of NUC-1031 infusion. Optional urine pooled urine collections will be collected at the following visits:

- Cycle 1: Days 1 and 2
- Cycle 1: Days 15 and 16

Standard PK parameters for each compound of interest will then be derived from the measured plasma, urine and PBMC concentrations. The PK samples will be processed and analyzed at a central laboratory. Please refer to the Guidelines for Pharmacokinetic Sample Management for details regarding PK sample collection, processing and shipping.

